5.2.5 Relative dose intensity (RDI)

Relative dose intensity (mg/day) = dose intensity (mg/day) / planned dose intensity (mg/day)

5.2.6 Mean relative dose intensity (mean RDI)

Mean relative dose intensity (mg/day) = mean of the relative dose intensity per patient by study treatment component

5.2.7 Adverse events of special interest

- Neutropenia = AE term: MedDRA Preferred Term “Neutropenia” (10029354)
- Hepatobiliary toxicity = AE term: MedDRA Preferred Term “Alanine aminotransferase increased” (10001551) or “Aspartate aminotransferase increased” (10003481), Toxicity grade “Grade 3” or “Grade 4”
- QT prolongation = AE term: MedDRA Preferred Term “Electrocardiogram QT prolonged” (10014387)

5.3 Programming rules

5.3.1 Calculation of ‘time to event’ variables

Time to event = end date - start date + 1 (in days).

When no post-baseline tumor assessments was available, the date of first application of treatment was used as end date (duration = 1 day) when time was to be censored at last tumor assessment, i.e. time to event variables can never be negative.

5.4 Imputation rules

5.4.1 Incomplete assessment dates

All investigation dates (e.g. X-ray, CT scan) must have been completed with day, month and year.

If one or more investigation dates was incomplete but other investigation dates were available, this/these incomplete date(s) was/were not considered for calculation of the assessment date (and assessment date was calculated as outlined in Section 3.2.7). If all measurement dates had no day recorded, the 1st of the month is used.

If the month was not completed, for any of the investigations, the respective assessment was considered to be at the date which is exactly between previous and following assessment. If a previous and following assessment was not available, this assessment was not used for any calculation.

5.4.2 Incomplete dates for last known date patient alive or death

All dates must have been completed with day, month and year. If the day was missing, the 15th of the month was used for incomplete death dates or dates of last contact.

5.4.3 Non-target lesion response

If no non-target lesions were identified at baseline (and therefore not followed throughout the study), the non-target lesion response at each assessment was considered ‘not applicable (NA)’.

5.4.4 Censoring reason

In order to summarize the various reasons for censoring, the following categories were calculated for each time to event variable based on the treatment completion page, the end of study page and the survival follow-up page.

For survival the following censoring reasons are possible:

- Alive
- Unknown/Lost to follow-up

For PFS and TTP (and therefore duration of responses) the following censoring reasons are possible:

- Ongoing without event
- Lost to follow-up
- Withdraw consent
- Adequate assessment no longer available*
- Event documented after two or more missing tumor assessments (optional, see Table 3-2)

- Death due to reason other than underlying cancer (*only used for TTP and duration of response*)
- Initiation of new anti-cancer therapy

*Adequate assessment is defined in Section 3.2.7. This reason was applicable when adequate evaluations were missing for a specified period prior to data cut-off (or prior to any other censoring reason) corresponding to the unavailability of two or more planned tumor assessments prior to the cut-off date. The following clarifications concerning this reason should also be noted:

- This may be when there has been a definite decision to stop evaluation (e.g. reason="Sponsor decision" on study evaluation completion page), when patients are not followed for progression after treatment completion or when only UNK assessments are available just prior to data cut-off).
- The reason "Adequate assessment no longer available" also prevails in situations when another censoring reason (e.g. withdrawal of consent, loss to follow-up or alternative anti-cancer therapy) has occurred more than the specified period following the last adequate assessment.
- This reason will also be used to censor in case of no baseline assessment.

5.4.5 Study treatment

In case of missing or partial start date, the start date should be shifted to the earliest possible date, but not earlier than the C1/D1 visit, i.e. the beginning of the on-treatment period, respectively not earlier than the previous administration. Missing or partial end dates (which result often from "ongoing" answers) should be shifted forward as far as possible: At maximum to the last documented on-treatment visit, i.e. C1/D1 to End-of-treatment-visit and not later than the following administration.

5.4.6 AE date imputation

In case of missing or partial start date or end date of an AE, the start date should be shifted to the earliest possible date, but not earlier than the first intake of study drug while the end date should be shifted forward as far as possible.

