1.2 Study objectives and endpoints

Objectives and related endpoints are described in the table below (in accordance with Table 3-1 from the protocol).

Primary Objective	Endpoint

The primary objective of this study is the assessment of the clinical benefit rate after 24 weeks for the total population and for cohorts A and B separately:
 
1. Cohort A: postmenopausal women and men who received no prior treatment for advanced disease. (70% group)2. Cohort B: pre-, and perimenopausal women who received no prior treatment for advanced disease as well as pre-, peri- and postmenopausal women and men who received no more than 1 prior chemotherapy and 2 prior lines of endocrine therapy for advanced disease (30% group)	Clinical Benefit Rate (CBR) after 24 weeks of treatment as defined by RECIST 1.1 as percentage of patients with CR, PR or SD until week 24 or longer as well as patients with NCRNPD >24 weeks for patients with non-measurable disease

Secondary Objectives	Endpoint

To assess the clinical benefit rate (CBR) after 24 weeks among Cohort B1 and B2:
	
Clinical Benefit Rate (CBR) after 24 weeks of treatment as defined by RECIST 1.1 as percentage of patients with CR, PR or SD until week 24 or longer as well as patients with NCRNPD >24 weeks for patients with non-measurable disease

Progression-free survival (PFS) for the three different populations: Cohort A, Cohort B1, Cohort B2
	
PFS based on radiologic assessment by investigator using RECIST 1.1 criteria (e.g. median PFS, PFS rate at 12 and 18 months)

Overall survival (OS) for the three different populations, defined as the time from date of start of treatment to date of death due to any cause.
	
Overall survival (OS) (e.g. OS rate at 12 and 24 months)

Overall response rate (ORR) for the three different populations, defined as complete response or partial response as defined by RECIST 1.1
	
Overall Response Rate (ORR) after 24 weeks

To evaluate the safety and tolerability of ribociclib in combination with letrozole (and goserelin in premenopausal patients)
	
Frequency/severity of AEs AEs of special interest: Frequency, severity, frequency per patient, time to Event, duration of Event and recurrence

To evaluate patient reported outcomes for health related quality of life
	
Laboratory values Time to 10% deterioration in the global health status/QOL scale score of the EORTC QLQ-C30

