2.8.1 Adverse events (AEs)

Summary tables for adverse events (AEs) include only AEs that started or worsened during the on-treatment period plus 30 days, the **treatment-emergent** AEs. However, all safety data (including those from the pre and post-treatment periods) will be listed in CSR section 16.2. Absolute and relative frequencies for patients with AEs collected during the pre-treatment and post-treatment period are presented.

The following analyses are presented for the different types of AEs:

	Incidence (frequency table)	Two-level frequency table SOC x PT (MedDRA)	Patient data Listing (section 14.3.1)	Maximum severity (frequency table)	Time to event	Dur- ation of event	Recurrence/ frequency of events per patient
Treatment emergent AEs	X	X		X			
Treatment emergent serious AEs	X	X	X	X	X	X	X
Treatment emergent non-serious AEs	X	X					
TEAE with suspected drug relation to ribociclib	X	X					
TEAE leading to permanent discontinuation of study drug	X	X					
TEAE of special interest	X	x	x		X	X	X
Death (in pre-/on-/post-treatment period)	X		X				

The **incidence frequency table** presents the number, percentage and 95% confidence for occurrence of at least one event of the respective AE type. This table is separated by each of the observation period (pre-/on-/post-treatment) and total. Denominator (for each period) is the number of patients in the Safety Analysis Set (SAF).

The **two-level frequency table** calculates absolute and relative frequencies for MedDRA System Organ Classes (SOC) and Preferred Terms (PT) within SOCs. Again, the number of patients in SAF is used as denominator and each event is counted only once in the respective category. The MedDRA version currently available at time point of analysis is used for decoding.

The **frequency table for maximum severity** analyses the maximum CTC-AE grade and display n and % for each category (total, SOC, and PT). Again, the number of patients in SAF is used as denominator and each maximum severity is counted only once in the respective category.

All patient data are listed in CSR section 16.2. Additionally **data listings** relevant for safety assessment are presented in section 14.3.2. Here, the patient identification, the verbatim term given by the investigator, MedDRA preferred term and system organ class, start/end dates,

severity, seriousness, relationship to study drug and action taken are listed. The AE onset will also be shown relative (in number of days) to the date of initial dose.

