
2.8.1.1 Adverse events of special interest / grouping of AEs

The following (S)AEs of special interest were defined:

- Neutropenia (MedDRA Code 10029354)
- Hepatobiliary toxicity, defined as grade 3 or 4 increases in ALT or/and AST (MedDRA Codes: 10001551, 10003481)
- QT prolongation (MedDRA Code 10014387)

In addition, the time to occurrence from start of study drug to the (first) onset of a TEAE of special interest (TEAESI) is analysed by sample statistics as well as the duration (start – end + 1 day). Further the number of TAEASI occurring in one patients during on-treatment period is displayed.

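### AE end-date imputation has no named upper bound and feeds uncensored SAE and AESI duration summaries, so reported durations are biased in a direction that depends on why the end date is missing

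*SAP*

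**What the plan says.** SAP 5.4.6 covers missing or partial AE dates. The start is moved back as far as possible, "while the end date should be shifted forward as far as possible". The start has a limit (first drug intake); the end has none.

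SAP 5.4.5, the neighbouring rule for dosing dates, uses the same idea but adds limits: the end date "should be shifted forward as far as possible: At maximum to the last documented on-treatment visit", and it may not pass the next administration.

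The imputed AE dates feed reported results:

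- SAP 1.2 lists, as a safety endpoint, "AEs of special interest: Frequency, severity, frequency per patient, time to Event, duration of Event and recurrence".
- The table in SAP 2.8.1 marks a duration analysis in the row "Treatment emergent serious AEs" and in the row for AEs of special interest (AESIs).
- SAP 2.8.1.1 says that time to the first AESI "is analysed by sample statistics as well as the duration", and prints the duration formula as start − end + 1 day. No method is named for SAE duration.

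SAP 5.4.4 defines censoring reasons for survival, PFS, TTP and duration of response. AE duration is not among them. Protocol 8.1.1 allows AE outcomes of not resolved and resolving, so AEs without an end date are to be expected.

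**The concern.** Choosing the latest possible end date is cautious when the question is whether an event overlaps a period. It is not cautious when the end date is itself the outcome, because the imputed value then becomes the result. Two different kinds of incomplete event go through the same rule: events that ended on a date nobody recorded, and events that had not ended. Neither is separated from fully observed events in a plain mean and median.

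At stake is how the plan describes the length of neutropenia, ALT/AST rises and QT prolongation, the three AESIs. The trial is single-arm and aims at estimation, so there is no comparator in which the same bias would cancel. Without a named bound, two programmers could also follow 5.4.6 correctly and report different durations.

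**Working it through.** The plan states no figure for AE duration, so there is none to reproduce. The share of AEs with incomplete end dates is not given either. Everything below that uses a share is an illustration.

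**Inputs.** From Protocol 7.2.2.4.2 (earlier phase III trial, grade 3 or higher ALT/AST rises): median time to resolution 24 days, median ALT onset day 57. From Protocol 7.1.3.1: treatment planned to 80 weeks after the last patient's first dose, plus 30 days of safety follow-up, so 80 × 7 + 30 = 590 days, taken here as an assumed latest date. Duration is end − start + 1.

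**1. The unnamed bound decides the answer.** For one AE starting on day 57 with no end date:

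| Bound chosen | Duration (days) |
|---|---|
| End-of-treatment visit, day 168 (assumed) | 168 − 57 + 1 = 112 |
| That visit + 30 days | 198 − 57 + 1 = 142 |
| 80 weeks | 560 − 57 + 1 = 504 |
| 80 weeks + 30 days | 590 − 57 + 1 = 534 |

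**2. Only the day is missing.** With the true day uniform over a 30-day month, moving it to day 30 adds 30 − 15.5 = 14.5 days on average and 29 at most. Assume log-normal durations with median 24 and log SD 0.8, so that the mean is 24 × exp(0.8²/2) ≈ 33.1 days. If 10% of dates lack the day, the mean rises by 1.45 days (1.45/33.1 ≈ 4%); if 20%, by 2.9 days (≈ 9%). Moving a partial start date to its earliest possible value lengthens the duration further.

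**3. Event resolved, whole end date lost.** Simulation with exponential durations (median 24) and exponential onset (median 57), lost dates set to day 590. Mean time from onset to day 590 is about 590 − 57/ln 2 ≈ 508 days, so for a lost share f the mean is about (1 − f) × 34.5 + f × 508. At f = 10% this is 31.05 + 50.8 ≈ 82, as simulated.

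| Share lost (assumed) | Mean (days) | Median (days) |
|---|---|---|
| 0% | 34.5 | 23.9 |
| 5% | 58.4 | 25.8 |
| 10% | 82.0 | 28.0 |
| 20% | 129.3 | 33.9 |
| 40% | 224.5 | 61.9 |

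At low shares the mean moves far more than the median.

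**4. Event truly unresolved.** With longer events (exponential, median 180 days, assumed) and the same cut-off, 15.1% are still ongoing at day 590. Counting them as ended there gives a mean of 221.2 days against a true 260.3, and a median of 178.6 against 180.3. Duration is understated. A Kaplan-Meier analysis that censors them gives a median of 180.3, matching the truth.

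**5. The summary cannot tell the two apart.** If 20% of the short events never resolve and are ended at day 590, the mean is 129.7 and the median 33.9. Step 3 at 20% gives almost the same pair, 129.3 and 33.9. In step 3 the mean is nearly four times the truth. Here the observed time is only a lower bound for the events that were cut off.

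**6. Formula.** As printed, an event from day 57 to day 80 has duration 57 − 80 + 1 = −22. The intended value is 80 − 57 + 1 = 24.

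**The case against.** A reader might infer that ongoing events enter at maximal length and inflate the reported durations, perhaps by a large percentage of the mean. The documents do not support that. SAP 5.4.6 does not mention ongoing events; the remark that missing end dates often come from ongoing answers is in 5.4.5 and concerns dosing. An event still present at last contact or cut-off has lasted at least that long, so ending it there shortens it (step 4). Inflation would need an end date beyond death, last contact or cut-off, which the text neither requires nor excludes. No percentage can be given for the net effect, because the share of incomplete dates is unknown.

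Other points against the concern:

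- Incomplete dates may be few. Start and end dates are collected for each AE and events are followed until resolved or judged permanent (Protocol 8.1.1), and missing values are queried (Protocol 9.4). This stands, and is a reason not to assume high shares.
- When only the day is missing, the recorded month is itself a bound. This stands; the missing limit matters for wholly missing dates.
- The safety endpoint in Protocol Table 3-1 is frequency and severity; duration is added in SAP 1.2. SAP 2.1 also reports the median, which is less affected at low shares. Both stand, and limit the importance of the point.
- SAP 2.1 assigns Kaplan-Meier to time-to-event data in general. This does not help for AESIs, because 2.8.1.1 specifies sample statistics for them. For SAEs the plan leaves it open.

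**Conclusion.** The point holds in a limited form. The AE end-date rule has no named upper bound, and it feeds duration summaries with no censoring rule. Resolved events with an incomplete end date are lengthened: 14.5 days on average when only the day is missing, or about 4% to 9% on the mean if 10% to 20% of dates are affected (assumed shares and an assumed log-normal distribution). A wholly missing date adds more, by an amount set by whichever bound the programmer picks. Unresolved events counted as complete are understated. The direction of the net bias depends on why dates are missing, and its size cannot be stated from the documents. The simulated means in steps 3 to 5 show the mechanism and are not estimates for this trial.

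The primary endpoint and the other efficacy results are unaffected. A listed safety endpoint is not reproducible as written, and the remedy is cheap, so the SAP should be changed.

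**What to change.** 1. In SAP 5.4.6, cap every imputed AE end date at the earliest of death, last contact and data cut-off, and say how events marked as ongoing are handled.
2. Use latest-possible end dates for classification only, not for duration.
3. For SAE and AESI duration, censor events that are unresolved or have no end date, and report a Kaplan-Meier median; or summarise resolved and unresolved events separately, with counts of each. Censor at the last AE assessment at which the event was still recorded as present. For an event that resolved on an unknown date, censoring at the cut-off would keep the same excess time.
4. Where only the day is missing, name one convention. Mid-month, already used for death dates in SAP 5.4.2, roughly centres the error (15 − 15.5 = −0.5 days in a 30-day month). It should not precede onset or pass the cap.
5. In SAP 2.8.1.1, change the formula to end − start + 1, and name the method for SAE duration as well.

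The cost is SAP wording, minor programming and a rerun of any duration tables already produced. No new data are needed.

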5.4.7 Concomitant medication date imputation

In case of missing or partial start date or end date of a concomitant medication, the start date should be shifted to the earliest possible date, but not earlier than the first intake of study drug while the end date should be shifted forward as far as possible.

5.4.7.1 Prior antineoplastic therapies date imputation

In case of missing or partial start date or end date of a prior therapy, the start date should be shifted to the earliest possible date, but not earlier than the initial diagnosis while the end date should be shifted as far back as possible, but not later than the first intake of study drug.

5.4.7.2 Post antineoplastic therapies date imputation

In case of missing or partial start date or end date of a post therapy, the start date should be shifted to the earliest possible date, but not earlier than the first intake of study drug while the end date should be shifted forward as far as possible.

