2.5 Analysis of the primary objective

2.5.1 Primary endpoint

The primary objective of this study was the assessment of the clinical benefit rate after 24 weeks.

The **Clinical Benefit Rate (CBR)** is the proportion of patients with a best overall response of confirmed complete (CR) or partial (PR) response or stable disease (SD) or non-complete response, non-progressive disease (NCRNPD) within Week 24. The best overall response for

each patient is determined from the sequence of investigator overall lesion responses until week 24 according to RECIST 1.1. To be assigned a best overall response of CR at least two determinations of CR at least 4 weeks apart before progression are required. To be assigned a best overall response of PR at least two determinations of PR or better at least 4 weeks apart before progression (and not qualifying for a CR) are required. To be assigned a stable disease, two determinations of SD at least 12 weeks apart (and not qualifying for PR or CR) are required.

Patients with best overall response “unknown” will be summarized by reason for having unknown status. The following reasons will be used:

- No valid post-baseline assessment
- All post-baseline assessments have overall response UNK
- New anti-neoplastic therapy started before first post-baseline assessment
- SD too early (≤ 6 weeks after randomization)
- PD too late (>12 weeks after randomization and not qualifying for CR, PR, or SD)

Special (and rare) cases where BOR is unknown due to both early SD and late PD will be classified as “SD too early”

During data review. i.e. before analysis, the number and reasons for best responses falling into the category “unknown” according to RECIST 1.1 criteria are investigated. In addition, the impact of confirmation of response on the outcome in the context of the visit schedule and assessment timepoints will be assessed. If necessary, further sensitivity analyses were defined to adjust for this uninformative category.

Any discontinuation due to ‘Disease progression’ without documentation of progression by RECIST criteria will be carefully reviewed during the data review meeting. Only patients with documented deterioration of symptoms indicative of progression of disease should have this reason for discontinuation of treatment or study evaluation.

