2.5.3 Handling of missing values/censoring/discontinuations

Since the definition of the primary variable was derived from tumor assessments based on RECIST 1.1 criteria, these criteria apply for the handling of missing values in tumor assessments. The evaluation of overall lesion response at each assessment is a composite of the target lesion response, non-target lesion response and presence of new lesions (see protocol, Post-text supplement 1). If the evaluation of any of the target or non-target lesions identified at baseline could not be made during follow-up, the overall status must be 'unknown' unless progression was seen. Patients with a best overall response assessment of unknown (UNK) were not be regarded as 'responders' but were included in the denominator for the calculation of the ORR for the FAS.

For patients who took other anti-neoplastic drugs their efficacy data will be censored so that the tumor assessments made after the administration of the other anti-neoplastic drugs are not included in the primary efficacy analyses. Sensitivity analysis including these observations may be performed if decided during data review meeting.

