2.7.3 Handling of missing values/censoring/discontinuations

Same instructions as for primary analysis

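### Incomplete start dates of post-study anticancer therapy can be imputed back to the first study dose; if the exclusion rule uses such dates, valid on-treatment scans are lost

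*SAP*

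**What the plan says.** - **Imputation (SAP 5.4.7.2).** When the beginning of a later anticancer treatment is incompletely dated, the rule reads: "the start date should be shifted to the earliest possible date, but not earlier than the first intake of study drug". No other lower bound is given.
- **Exclusion (SAP 2.5.3).** For patients who took other anti-neoplastic drugs, "the tumor assessments made after the administration of the other anti-neoplastic drugs are not included in the primary efficacy analyses". For the secondary efficacy endpoints SAP 2.7.3 says "Same instructions as for primary analysis", and SAP 5.4.4 lists new anti-cancer therapy among the PFS censoring reasons.
- **Unknown response (SAP 2.5.1, 2.5.3).** One listed reason for an unknown best response is "New anti-neoplastic therapy started before first post-baseline assessment"; having no valid post-baseline assessment is another. "Patients with a best overall response assessment of unknown (UNK) were not be regarded as" responders, but they stay in the FAS denominator. That sentence names the ORR; for the CBR, unknown is simply not among the benefit categories.
- **Stable disease (SAP 2.5.1).** It requires "two determinations of SD at least 12 weeks apart". SAP 5.1.1 schedules two post-baseline scans by week 24.
- **What a post therapy is (protocol 7.1.4).** New anticancer therapies given after the last ribociclib dose. Protocol Table 14-1 requires study drug to stop if other anticancer treatment is needed.
- **Last dose (SAP 5.2.1).** The last ribociclib date is taken from the Treatment Completion CRF.

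**The concern.** A therapy recorded as following the last ribociclib dose should not be dated before that dose, yet the stated floor allows it to be placed on the day treatment began. The neighboring rules use bounds that fit their context: initial diagnosis for prior therapies (SAP 5.4.7.1) and the previous administration for study drug (SAP 5.4.5). The post-therapy rule instead repeats the first-intake floor used for adverse events and concomitant medication.

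The date matters because the exclusion rule needs one. If an imputed date is used, scans taken under study drug are treated as taken under another therapy. The primary endpoint and two secondary endpoints would then depend on how completely a later event was dated.

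**Working it through.** **1. The plan's own precision, for scale.** The Wald interval is p ± 1.96·√(p(1−p)/n). With p = 0.79 and n = 500 it gives 75.43% to 82.57%, width 7.14 points. SAP section 3 states 75.4% to 82.6%, width 7.2, so the figure is reproduced to rounding. The half-width is 3.57 points. The planned Clopper-Pearson interval is slightly wider (7.33 points).

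**2. One patient followed through the rules (dates are my assumption).** First dose 1 March 2017. Stable disease on 24 May, 16 August and 8 November 2017 (weeks 12, 24 and 36). Progression on 31 January 2018 (week 48). Last dose 5 February 2018, then another therapy. PFS time is end date − start date + 1 (SAP 5.3.1).

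| Recorded start of new therapy | Imputed date, SAP as written | Post-baseline scans kept | Week-24 result | PFS |
|---|---|---|---|---|
| Wholly missing | 1 Mar 2017 | 0 of 4 | Unknown | Censored, day 1 |
| Year only (2018) | 1 Jan 2018 | 3 of 4 | Benefit | Censored, day 253 |
| Month known (Feb 2018) | 1 Feb 2018 | 4 of 4 | Benefit | Event, day 337 |

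With a floor at the day after the last dose (6 February 2018), the first two rows also keep all four scans, the week-24 benefit and the event at day 337.

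A year-only date in the year of first dose behaves like a missing one. Had this patient stopped in autumn 2017 with a start recorded only as 2017, 1 January 2017 precedes the first dose. The floor then binds at 1 March 2017 and both scans needed for stable disease are lost.

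**3. Effect on the CBR.** Patients who progressed without benefit count as non-benefit whether labeled PD or unknown, so only those with true benefit matter, and the error can only be downward. For k such patients the loss is k/N. The values of k are assumed, because the documents give no count.

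| k of 500 | CBR | Exact 95% CI |
|---|---|---|
| 0 | 79.0% | 75.2 to 82.5 |
| 5 | 78.0% | 74.1 to 81.6 |
| 10 | 77.0% | 73.1 to 80.6 |
| 25 | 74.0% | 69.9 to 77.8 |

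The k that equals the planned half-width is 0.0357 × 500 = 17.85, about 18 patients (3.6%). In cohort B (n = 150, planning CBR 67%) the Wald half-width is 1.96·√(0.67 × 0.33/150) = 7.52 points, or about 11 patients. Starting from 100/150 = 66.7%, k = 3 gives 64.7% and k = 8 gives 61.3%.

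**4. Effect on PFS.** The first two rows of the patient table turn an observed progression into censoring. This happens only in patients who moved to another therapy, so the censoring is informative and may raise the Kaplan-Meier curve. OS is unaffected.

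**The case against.** The strongest reply is that the chain has an inferred link. SAP 2.5.3 speaks of drugs administered and does not mention imputed dates. The variable-level definitions of CBR and PFS in SAP 5.1.1 and 5.1.3 contain no therapy start date. This stands as a limit on certainty. But the exclusion needs a date, the imputation is not restricted to any purpose, and nothing exempts imputed dates.

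A second reply is that the earliest possible date for a post therapy is already after the last dose. If so, the stated floor would never bind for these records. A programmer following the text would use first intake. It is fair to add that protocol 10.1.3 anticipates other anti-neoplastic therapy started on study before the first tumor assessment, so a true start before the last dose is not impossible. The fix must leave room for it.

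Third, there are safeguards: site queries for missing values (protocol 9.4), pre-analysis review of unknown responses (SAP 2.5.1) and an optional sensitivity analysis that keeps the excluded scans (SAP 2.5.3). They may expose affected patients, but none corrects the primary derivation.

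Some stronger inferences do not hold:

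- **That every incomplete date does harm.** A missing day moves the date by at most 30 days.
- **That every affected patient is censored at day 1 for PFS.** SAP 5.1 also takes progression from the disposition page, and deaths are events under SAP 5.1.3.
- **That the similar floor in SAP 5.4.7 distorts a table of medication taken before study start.** SAP 2.4.2 specifies no such separate table, and no efficacy result depends on that rule.

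**Conclusion.** The point holds as a defect in a stated rule, conditional on imputed dates feeding the exclusion in SAP 2.5.3. The harm is confined mainly to wholly missing dates and to year-only dates in the year of first dose. A later year-only date can still turn a progression into censoring. CBR and ORR can only be lowered; PFS may be raised.

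The CBR loss is k/N. If 1% of the FAS were affected and all of them had true benefit, the loss would be 1.0 point. A reader might scale this by the planning CBR of 79% and infer 0.8 points per 1%. The documents do not support that, either as a bound or as an expectation, because patients who left study drug for another therapy are a selected group that includes early progressors. The actual size cannot be determined, since the frequency of such dates is not given.

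**What to change.** In SAP 5.4.7.2:

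1. Set the floor for an incomplete start date at the day after the last ribociclib administration, taken from the Treatment Completion CRF. Use ribociclib rather than study treatment as a whole: that term includes goserelin, which SAP 5.2.1 says may continue with follow-up therapy.
2. Impute within any recorded month or year. Where a recorded partial date lies wholly before the floor, do not override it; query it and settle it at the data review meeting.
3. State that imputed dates trigger the exclusion in SAP 2.5.3, and through 2.7.3 the secondary endpoints, only under this floor.

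The cost is a few sentences in the SAP and a small programming change; no new data are needed. If analyses have already been run, count the patients whose new-therapy start was imputed before their last ribociclib dose, and re-derive CBR, ORR and PFS if there are any.
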